## 7.2 SAMPLE SIZE:

7.2.1 PRIMARY SAFETY OBJECTIVE: The study is designed to test the null hypothesis that the acute and late GI/GU toxicity rate 2 years following treatment is less than 10% versus the alternative hypothesis that the toxicity rate is greater than or equal to 10%. If we end up with 200 eligible patients, there will be 99% probability, or statistical power, of identifying excessive toxicity if the true

toxicity rate is 20%, at the one-sided significance level ( $\alpha$ ) 0.05. The intervention will be considered to be safe if the acute and late GI/GU toxicity rate 2 years following treatment is not above 10%

7.2.2 PRIMARY EFFICACY OBJECTIVE: The study is powered to compare 2-year bDFS rates observed with SBRT to 2-year bDFS rates reported with dose-escalated external beam RT. In Beaumont's monotherapy HDR series treating patients, 5-yr ASTRO bDFS was 97.5%; in Demanes' series of 75% LR and 25% IR, this was 96%. We would expect Phoenix outcomes to be slightly higher than ASTRO outcomes at 5 years. Since SBRT delivers doses similar to HDR monotherapy, a conservative estimate of the success rate for SBRT is 97.5%. In LR patients, prospective studies from Memorial Sloan Kettering (203 patients, 81Gy) and MD Anderson (32 patients, 78Gy) demonstrated 5-yr bDFS (Phoenix definition) of 92% and 92%, respectively. Thames' 9-institution review of 231 dose-escalated (70-76Gy) LR patients reported 94% 5-yr Phoenix bDFS. Thus, an objective performance criteria (OPC) for low-risk patients treated with dose-escalated external beam RT is 92% 5-yr bDFS. If we assume the SBRT success rate is 97%, a sample size of 200 patients will provide 99% power to test superiority of SBRT against this OPC with 80% power at the 1-sided 5% significance level. If we assume the SBRT success rate is 96%, then the power will be 78%.

7.2.3 TOTAL AND RELATIVE ENROLLMENT: Per above sections 7.2.1-7.2.2, we plan to accrue 200 eligible patients to compare the 2-year bDFS rate observed with SBRT to the 2-year OPC rate, and to establish acceptable toxicity. The test cohort will be closed to accrual once requisite enrollment is achieved: 200 total patients.

7.2.4 ACCRUAL RATE: The accrual rate will be 5–6 patients / month over 2 years.

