### 7.3.1 PRIMARY ENDPOINTS:

Wilson score interval is used to determine the confidence intervals for the expected proportion of patients experiencing a “success” outcome.

7.3.1.1 SAFETY: The upper limit of a one-sided 95% confidence interval for the expected proportion of patients experiencing any grade 3-5 acute or late toxicity as defined above in 7.1, is estimated by U, where

$$U = \frac{(2np + Z_{0.95}^2) + Z_{0.95} \sqrt{Z_{0.95}^2 + 4np(1-p)}}{2(n + Z_{0.95}^2)}$$

where:

p: the observed proportion of patients experiencing any grade 3-5 acute or late toxicity as defined above in 7.1;  
n: the total number of patients;  
 $Z_{0.95} = 1.645$ .

The intervention will be considered to be safe if this study’s result verifies that U is not above 10%i.

7.3.1.2 EFFICACY: The lower limit of a one-sided 95% confidence interval for the expected proportion of patients experiencing biochemical disease-free survival (bDFS) is estimated by L, where

$$L = \frac{(2np + Z_{0.95}^2) - Z_{0.95} \sqrt{Z_{0.95}^2 + 4np(1-p)}}{2(n + Z_{0.95}^2)}$$

where:

p: the observed proportion of patients experiencing bDFS;  
n: the total number of patients;  
 $Z_{0.95} = 1.645$ .

The SBRT intervention will be considered to be effective if this study’s result verifies that L is not below 92%.

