#### 7.4 **RULE FOR EARLY STOPPAGE BASED ON TOXICITY:**

The NCI Common Terminology Criteria for Adverse Events, version 3.0 (CTCAE V3.0) will be used to evaluate toxicity. We will consider a toxicity to be an adverse event that is possibly, probably or definitely related to the treatment. The maximum grade of toxicity for each category of interest will be recorded for each patient and the summary results will be tabulated by category and grade. We will describe all serious ( $\geq$  Grade 3)

AEs on a patient-by-patient basis; descriptions will include dose level and any relevant baseline data. The toxicity will be assessed every 10 patients.

For safety, we will consider that regimen to be excessively toxic and stop accrual if, at any time, the observed rate of grade 3-5 acute or late toxicity as defined above in  $7.1 \geq 33\%$  and at least 4 toxicities have been observed. Thus, we will stop accrual if:

[# of participants with toxicity] / [# of participants evaluated] =

[4]/[10],

[7]/[20],

[10]/[30],

[14]/[40]

[17]/[50]

[20]/[60]

[24]/[70]

[27]/[80]

[30]/[90]

[33]/[100]

[37]/[110]

[40]/[120]  
[43]/[130]  
[47]/[140]  
[50]/[150]  
[53]/[160]  
[57]/[170]  
[60]/[180]  
[63]/[190]  
[66]/[200]

The study design has the following properties: if the true rate of grade 3-5 acute or late toxicity as defined above in 7.1 toxicity in this participant population is  $\geq 42\%$ , there is at least 90% probability that accrual will stop; if the true grade 3-5 acute or late toxicity as defined above in 7.1, toxicity rate is  $\leq 8.7\%$ , there is 90% probability that the accrual will not stop, and that the regimen will be considered safe.

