## 8.0 Data Safety and Recording

### 8.1 Data safety monitoring plan

All patient data will be collected by the University of Pittsburgh Cancer Institute's Protocol Office. All data will be secured in a password protected file with observance of all applicable HIPAA regulation. A data safety monitoring board will meet monthly to evaluate toxicity for this trial. Patients/adverse events will be discussed at these monthly department meetings. Unexpected serious adverse events will be reported to the IRB and DSMC, and minutes of the monthly disease center meetings will be reviewed at the DSMC meetings. Headed by the PI, the sub-investigators of this protocol along with all radiation oncology medical staff and a study coordinator are in attendance at this meeting. There is also a quarterly meeting headed by the PI held with the collaborating surgeons trained in radiosurgery and a study coordinator. Any adverse events, changes in risk to benefit considerations for the study, and any breaches of confidentiality are discussed at these meeting as well.

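### Section 7.4 gives 90% probability of not stopping and being considered safe at a true toxicity rate of 8.7%; under the plan's own safety criteria it is about 16% or 78%, and the stopping figures are only loose bounds

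*Combined protocol and SAP*

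**What the plan says.** Section 7.4 stops accrual when the observed rate of grade 3-5 acute or late toxicity is at least 33% "and at least 4 toxicities have been observed". It lists 20 boundaries, from 4 of 10 to 66 of 200. On timing it says "The toxicity will be assessed every 10 patients", but it also words the rule as applying at any time.

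Its last paragraph states two properties of the design. At a true rate of 42% or more, "there is at least 90% probability that accrual will stop". At a true rate of 8.7% or less, "there is 90% probability that the accrual will not stop, and that the regimen will be considered safe".

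Section 7.4 gives no criterion for safe. Two other sections do:

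- Section 7.2.1: "The intervention will be considered to be safe if the acute and late GI/GU toxicity rate" two years after treatment does not exceed 10%.
- Section 7.3.1.1: the intervention counts as safe if the "result verifies that U is not above 10"%, where U is the one-sided 95% Wilson upper limit for the same grade 3-5 toxicity endpoint.

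**The concern.** The second property joins two events: accrual is not stopped, and the regimen is then considered safe. The second event depends on a criterion that 7.4 does not name. The wording is close to that of 7.3.1.1, where the upper limit, not the observed rate, must be at or below 10%. A true rate of 8.7% lies so near 10% that 200 patients will seldom push the upper limit below 10%. A 90% chance of being considered safe therefore looked implausible.

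The stopping figures raised a second question. 8.7% and 42% lie far apart, and 20%, the rate that 7.2.1 uses as its example of excessive toxicity, falls between them. These two sentences are the plan's only stated probabilities for the accrual rule. A safety committee or ethics board relying on them would not learn where the rule starts to act, and could believe that a regimen with 8.7% severe toxicity is very likely to pass the primary safety criterion.

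**Working it through.** **Inputs.** Boundaries b(k) at k = 10, 20, ..., 200 from 7.4; all equal max(4, 0.33k rounded up). n = 200 (7.2.3). Wilson formula with Z = 1.645 (7.3.1.1). Assumption: each patient's toxicity status is complete when he is counted.

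**Stopping probability.** Let f(k, x) be the probability that accrual has not stopped and x of the first k patients have had toxicity. Then

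f(k, x) = (1 − p) f(k−1, x) + p f(k−1, x−1).

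At each look the mass with x ≥ b(k) is removed and added to P(stop). A hand check at the first look: P(X ≥ 4 | n = 10, p = 0.087) = 0.0078, which is most of the total of 0.0084.

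| True rate | P(stop), looks every 10 patients | P(stop), check after every patient |
|---|---|---|
| 8.7% | 0.8% | 1.8% |
| 10% | 1.4% | 3.0% |
| 15% | 6.3% | about 12% |
| 20% | 18% | 28% |
| 25% | 39% | 51% |
| 30% | 70% | 78% |
| 42% | 99.9% | 99.97% |
| Rate at which P(stop) = 10% | 17.1% | 14.3% |
| Rate at which P(stop) = 90% | 33.8% | 32.7% |

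So the plan's 90% is not reproduced as a value at either rate. Not stopping at 8.7% has probability 1 − 0.0084 = 99.2%, and stopping at 42% has probability 99.9%. As lower bounds, both are true.

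**Counts that meet each safety criterion at n = 200.** Here Z² = 2.706, and the Wilson denominator is 2(200 + 2.706) = 405.41.

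- 13 toxicities: U = (26 + 2.706 + 1.645 × √(2.706 + 4 × 13 × 0.935)) / 405.41 = (28.706 + 11.785) / 405.41 = 9.99%, which passes.
- 14 toxicities: U = (28 + 2.706 + 1.645 × √(2.706 + 4 × 14 × 0.93)) / 405.41 = (30.706 + 12.176) / 405.41 = 10.58%, which fails.
- Section 7.3.1.1 therefore allows at most 13.
- Section 7.2.1, read as an observed rate not above 10%, allows at most 0.10 × 200 = 20.

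**Joint probability at a true 8.7%.** This is the sum of f(200, x) over the passing counts, with looks every 10 patients.

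| Criterion | Passing count | Not stopped and safe at 8.7% | True rate at which it is 90% |
|---|---|---|---|
| 7.3.1.1, U not above 10% | at most 13 | 16.4% | about 4.8% |
| 7.2.1, observed rate not above 10% | at most 20 | 78.2% | about 7.7% |

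The stopping rule plays almost no part in these figures. The plain binomial P(X ≤ 13 | n = 200, p = 0.087) is also 16.4%. Checking after every patient gives 16.3% and 77.7%. Because the plan's statement covers all rates up to 8.7%, it has to hold at 8.7%, where the joint probability is lowest.

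**The case against.** The strongest reply is that nothing in 7.4 is false if the section is read on its own. It sets excessively toxic, meaning stopped, against not stopped and safe. If safe means only not stopped, the probability at 8.7% is 99.2% and 90% is a valid floor. If safe means that the 7.2.1 null hypothesis is not rejected (exact test, at most 27 of 200), the joint probability is 98.4%, and again 90% is a floor. On this view the 16% comes from applying a final-analysis criterion to an accrual rule that does not cite it.

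Part of this stands. The 42% clause and the no-stop half of the 8.7% clause are true bounds, so a reader who infers that both stated stopping properties are wrong goes too far. But the plan nowhere defines safe as not stopped or as failing to reject. The two criteria that it does give both contradict the 90%.

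Three other readings go beyond the documents. A reader might infer that safe is undefined; it is defined twice, differently, and 7.4 points to neither. A reader might infer that the percentages were carried over from another design; the plan gives no source for them, and the correction does not need one. A reader might infer that a true 20% would go undetected; 7.2.1 states for the final analysis that "there will be 99% probability, or statistical power, of identifying excessive toxicity if the true" rate is 20%, and an exact test rejecting at 28 or more of 200 has 98.9% power. Section 8.1 adds that "A data safety monitoring board will meet monthly to evaluate toxicity for this trial".

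**Conclusion.** The concern holds in this limited form. The joint 90% at 8.7% is overstated under both safety criteria in the plan: about 16% under 7.3.1.1 and about 78% under 7.2.1 read as an observed rate. The separate stopping statements are correct but too loose to locate the rule, whose 10% and 90% stopping points are about 17% and 34% with looks every 10 patients.

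The joint figures hardly depend on how often the rule is checked; the stopping figures do, as the two columns show. All of them assume complete toxicity status when a patient is counted. Late toxicity begins more than 90 days after treatment and is followed to 24 months, so stopping during accrual could be less likely than shown.

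This is a wrong description of the design. It does not alter any boundary, the sample size or the final safety decision, so it should be fixed but does not threaten the trial.

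**What to change.** 1. Confirm that the listed boundaries, with the minimum of four toxicities, are the intended rule, and reconcile the two statements in 7.4 about when it is checked.
2. Replace the last paragraph of 7.4 with the stopping probabilities from the matching column of the first table, including the rates at which stopping reaches 10% and 90%. State that they assume complete toxicity status for each patient counted, and that stopping during accrual could be lower while late toxicity is still unobserved.
3. Delete the clause about the regimen being considered safe, or name one criterion and give its joint probability. If it is kept, bring 7.2.1, 7.3.1.1 and 7.4 into agreement on what safe means.

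No boundary or threshold is proposed here; that choice stays with the sponsor. The cost is one rewritten paragraph, plus a cross-reference if a criterion is named, with no extra patients, looks or data. The downside is that the new text shows openly that the rule seldom stops accrual at a true 20% (18%, or 28% if checked after every patient), and the sponsor may be asked to justify that.

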## 8.0 Data Safety and Recording

### 8.1 Data safety monitoring plan

All patient data will be collected by the University of Pittsburgh Cancer Institute's Protocol Office. All data will be secured in a password protected file with observance of all applicable HIPAA regulation. A data safety monitoring board will meet monthly to evaluate toxicity for this trial. Patients/adverse events will be discussed at these monthly department meetings. Unexpected serious adverse events will be reported to the IRB and DSMC, and minutes of the monthly disease center meetings will be reviewed at the DSMC meetings. Headed by the PI, the sub-investigators of this protocol along with all radiation oncology medical staff and a study coordinator are in attendance at this meeting. There is also a quarterly meeting headed by the PI held with the collaborating surgeons trained in radiosurgery and a study coordinator. Any adverse events, changes in risk to benefit considerations for the study, and any breaches of confidentiality are discussed at these meeting as well.

#### 8.1.1 Subject Removal Criteria

1. Disease progression
2. Development of a serious medical illness
3. Evidence of dose-limiting toxicity
4. Voluntary withdrawal
5. Protocol violation
6. Discretion of the principal investigator
7. Development of grade 4 toxicity related to experimental therapeutic

## 8.2 Safety Reporting

### 8.2.1 Acute Adverse Events

The CTCAE (described below) will be used to grade acute toxicity during this trial.

**CTCAE term (AE description) and grade:** The descriptions and grading scales found in the revised NCI Common Terminology Criteria for Adverse Events (CTCAE) version 3.0 will be utilized for AE reporting. All appropriate treatment areas will have access to a copy of the CTCAE version 3.0. A copy of the CTCAE version 3.0 can be downloaded from the CTEP web site (<http://ctep.cancer.gov>).

An AE is any untoward medical occurrence in a patient or clinical investigation subject administered a pharmaceutical product that does not necessarily have a causal relationship with this treatment. An AE can therefore be any unfavorable and unintended sign (including an abnormal laboratory finding), symptom, or disease temporally associated with the use of a medicinal (investigational) product, whether or not related to the medicinal (investigational) product.

It may include worsening or increase in severity of signs or symptoms of the illness, increase in frequency of signs and symptoms of an intermittent illness, or the appearance of a new manifestation/complication.

Exacerbation of a pre-existing illness should be considered when a subject requires new or additional concomitant drug or non-drug therapy for the treatment of that illness during the study. Lack of or insufficient clinical response, benefit, efficacy, or therapeutic effect should not be recorded as an adverse event. The investigator must make the distinction between exacerbation of pre-existing illness and lack of therapeutic efficacy.

In addition, abnormal objective test findings (e.g., abnormal laboratory test results, physical evaluation) that can result in a change in study treatment dosage or in discontinuation of the treatment, or require intervention or diagnostic evaluation to assess the risk to the patient, should also be recorded as adverse events. Clinically significant changes in physical examination findings should also be recorded as adverse events. For all adverse events, the investigator must pursue and obtain information adequate both to determine the outcome of the adverse event and to assess whether it meets the criteria for classification as a serious adverse event requiring immediate notification to UPCI or its designated representative.

*All observed or volunteered adverse events regardless of treatment group or suspected causal relationship to study treatment will be recorded on the adverse event page(s) of the CRF. The investigator will record all adverse events in the CRF and assess each event as to severity and causal relationship to study treatment.*

**‘Expectedness’:** AEs can be ‘Unexpected’ or ‘Expected’ for expedited reporting purposes only.

**Attribution** of the AE:

Definite – The AE is *clearly related* to the study treatment.

Probable – The AE is *likely related* to the study treatment.

Possible – The AE *may be related* to the study treatment.

Unlikely – The AE is *doubtfully related* to the study treatment.

Unrelated – The AE is *clearly NOT related* to the study treatment.

For all adverse events, sufficient information should be obtained by the investigator to determine the causality, (i.e., study treatment or other illness). The investigator is required to assess causality and indicate that assessment on the CRF. Follow-up of the adverse event, after the date of therapy discontinuation, is required if the adverse event or its sequelae persist. Follow-up is required until the event or its sequelae resolve or stabilize at a level acceptable to the investigator. Adverse events that continue, or emerge within 30 days, after the patient’s discontinuation or completion of the study will be followed until the events resolve, are considered stable, or can be ascribed to causes other than study treatment.

All serious AE shall be reported meeting criteria for reporting can be found on the University of Pittsburgh Institutional Review Board’s website at <http://www.irb.pitt.edu>. In the event of such adverse event, the investigator must report the event(s) via phone within 24 hours and a written report filed within 24 hours to the Principal Investigator, or the UPCI’s Clinical Research Office.

---

## Appendix I: ECOG PERFORMANCE SCALE

- 0 Fully active, able to carry on all predisease activities without restriction (*Karnofsky 90-100*).
- 1 Restricted in physically strenuous activity but ambulatory and able to carry out work of a light or sedentary nature. For example, light housework, office work (*Karnofsky 70-80*).
- 2 Ambulatory and capable of all self-care but unable to carry out any work activities. Up and about more than 50% of waking hours (*Karnofsky 50-60*).
- 3 Capable of only limited self-care, confined to bed or chair 50% or more of waking hours (*Karnofsky 30-40*).
- 4 Completely disabled. Cannot carry on any self-care. Totally confined to bed or chair (*Karnofsky 10-20*).

## Appendix II: AJCC STAGING SYSTEM, 6TH EDITION, PROSTATE

### *Primary Tumor, Clinical (T)*

- TX Primary tumor cannot be assessed
- T0 No evidence of primary tumor
- T1 Clinically inapparent tumor not palpable or visible by imaging
  - T1a Tumor incidental histologic finding in 5% or less of tissue resected
  - T1b Tumor incidental histologic finding in more than 5% of tissue resected
  - T1c Tumor identified by needle biopsy (*e.g., because of elevated PSA*)
- T2 Tumor confined with prostate\*
  - T2a Tumor involves less than ½ of one lobe
  - T2b Tumors involves greater than ½ of one lobe but < 2 lobes
  - T2c Tumor involves both lobes
- T3 Tumor extends through prostate capsule\*\*
  - T3a Extracapsular extension (*unilateral or bilateral*)
  - T3b Tumor involves the seminal vesicle(s)
- T4 Tumor is fixed or invades adjacent structures other than the seminal vesicles: bladder neck, external sphincter, rectum, levator muscles and/or pelvic wall

\*Note: Tumor found in one or both lobes by needle biopsy, but not palpable or reliably visible by imaging, is classified as T1c

\*\*Note: Invasion into the prostatic apex or into (*but not beyond*) the prostatic capsule is not classified as T3, but as T2.

### *Regional Lymph Nodes (N)*

- Clinical      NX Regional lymph nodes cannot be assessed
- N0 No regional lymph node metastasis
- N1 Metastasis in regional lymph node or nodes
- Pathologic    pNX Regional nodes not sampled
- pN0 No positive regional nodes
- pN1 Metastases in regional node(s)

### *Distant Metastasis (M)\**

MX Presence of distant metastasis cannot be assessed (not evaluated by any modality)

M0 No distant metastasis

M1 Distant metastasis

  M1a Nonregional lymph node(s)

  M1b Bone(s)

  M1c Other site(s) with or without bone disease

\*Note: When more than one site of metastasis is present, the most advanced category is used; pM1c is most advanced.

---

**Appendix III: AUA, FACT-G, EPIC, SHIM, USMD Questionnaires:**

**American Urological Association (AUA) symptom index:** was developed to help men determine how bothersome their urinary symptoms are and to check the effectiveness of treatment. This questionnaire has also been adopted worldwide and is known as the International Prostate Symptom Score (IPSS). It is sometimes seen with a Quality of Life Scale at the end of the questionnaire.

Name: \_\_\_\_\_ Today's date: \_\_\_\_\_

(Circle one number on each line)	Almost never	Less than 1 time in 5	Less than half the time	About half the time	More than half the time	Almost always
Over the past month or so, how often have you had a sensation of not emptying your bladder completely after you finished urinating?	0	1	2	3	4	5
Over the past month or so, how often have you had to urinate again less than two hours after you finished urinating?	0	1	2	3	4	5
Over the past month or so, how often have you found you stopped and started again several times when you urinated?	0	1	2	3	4	5
Over the past month or so, how often have you found it difficult to postpone urination?	0	1	2	3	4	5
Over the past month or so, how often have you had a weak urinary stream?	0	1	2	3	4	5
Over the past month or so, how often have you had to push or strain to begin urination?	0	1	2	3	4	5
	None	1 time	2 times	3 times	4 times	5 or more times

Over the past month, how many times did you most typically get up to urinate from the time you went to bed at night until the time you got up in the morning?	0	1	2	3	4	5
---	---	---	---	---	---	---

---

